10.3 Tumour response

All patients who meet the eligibility criteria and receive at least one cycle of trial medication and have a baseline assessment of disease will be evaluable for response. To be assigned a status of CR or PR, changes in tumour measurements must be confirmed by repeat measurements performed no less than four weeks after the response criteria are met. To be assigned a status of stable disease (SD), follow-up measurements must have met the SD criteria at least once and at least six weeks after the initial dose of the investigational medicinal product (IMP) is given.

Should rapid tumour progression occur before the completion of the first cycle of combination treatment (vandetanib and Selumetinib for 28 days) the patient will be classified as having early progression (EP).

Tumour response should be classified as “not evaluable” (NE), only when it is not possible to classify it under another response category, for example, when baseline and/or follow-up assessment is not performed or not performed appropriately.

Expert reviewers appointed by CDD may undertake an independent review of all the Investigator's assessed objective responses (CR and PR). The expert reviewers will include at least one specialist who is not an Investigator in the trial. In case of disagreement between the Investigator's and the expert reviewers' assessment, discussion will take place between the two parties in order to reach a consensus. However, if it is not forthcoming, the assessment of the expert reviewers will be retained in the clinical study report. The eCRF will reflect the Investigator's opinion.

Recording of response in the eCRF

The applicable overall response category for each visit that includes disease assessment must be recorded in the eCRF, even though the criteria for determination of CR or PR by the protocol must be confirmed after two consecutive observations, no less than four weeks apart.

Other definitions of outcome

Toxic death: Any death to which drug toxicity is thought to have a major contribution.

Early death: Death during the first 4 weeks of combination treatment (that is not a toxic death).

11 PATIENT WITHDRAWAL BEFORE COMPLETION OF TREATMENT SCHEDULE

The Investigator must make every reasonable effort to keep each patient on trial for the whole duration of the trial (i.e. until 28 days after last vandetanib and selumetinib administration). However, if the Investigator removes a patient from the trial or if the patient declines further participation, final 'off-study' assessments should be performed before initiating any new anti-cancer treatment.. All the results of the evaluations and observations, together with a description of the reasons for withdrawal from the trial, must be recorded in the medical records and in the eCRF.

Patients who are removed from the trial due to adverse events (clinical or laboratory) will be treated and followed according to accepted medical practice. All pertinent information concerning the outcome of such treatment must be recorded in the eCRF and on the serious adverse event (SAE) report form where necessary.

The following are justifiable reasons for the Investigator to withdraw a patient from trial.

- AE/SAE including unacceptable toxicity
- Withdrawal of consent
- Serious violation of the trial protocol (including persistent patient attendance failure and persistent non-compliance)
- Sponsor's decision to terminate the trial
- Withdrawal by the Investigator for clinical reasons not related to the IMP (vandetanib or selumetinib) including symptomatic deterioration
- Evidence of disease progression
- Pregnancy

12 DEFINING THE END OF TRIAL

The 'end of trial' is defined as the date when the last patient has completed the 'off-study' visit or the final follow-up visit (whichever is the latter).

It is the responsibility of the CDD to inform the Medicines and Healthcare products Regulations Agency (MHRA) and the Main Research Ethics Committee (REC) within 90 days of the 'end of the trial' that the trial has closed.

In cases of early termination of the trial (for example, due to toxicity) or a temporary halt by the CDD, the CDD will notify the MHRA and the Main REC within 15 days of the decision and a detailed, written explanation for the termination/halt will be given. The pharmaceutical company (Astra Zeneca) will also be informed of early termination/halt.

The entire trial will be stopped when:

- The drugs are considered too toxic to continue treatment before the required number of patients being recruited.
- The stated number of patients to be recruited is reached.
- The stated objectives of the trial are achieved.

Regardless of the reason for termination, all data available for the patient at the time of discontinuation of follow-up must be recorded in the eCRF. All reasons for discontinuation of treatment must be documented.

In terminating the trial, CDD and the Investigators must ensure that adequate consideration is given to the protection of the patient's interest.

13 DATA ANALYSIS AND STATISTICAL CONSIDERATIONS

The final analysis will be conducted after one of the following conditions is met.

- The trial is terminated early (for example, due to toxicity).
- All patients have completed their 'off-study' visit (i.e. 28 days after the last dose of vandetanib and selumetinib) and have been followed up for survival for one year from the first dose of IMP (Cycle 1 Day 1).

A clinical data cut-off date will be established to allow for primary analysis clinical study report (CSR) reporting once all recruited patients have been followed up for survival for a minimum of one year after the date of first IMP administration (Cycle 1 Day 1). The primary analysis CSR will include data from all treated patient visits/assessments up to and including the clinical cut-off date.

Any patients who continue to receive the combination therapy in the absence of disease progression or unacceptable toxicity after the clinical cut-off date will be included in an addendum to the final CSR. Only long-term safety data will be included in an addendum to the CSR.

PFS rate at 12 weeks will also be analysed for expansion cohort patients, according to the RECIST criteria. Assuming that the PFS rate in vandetanib alone is 9%, to test the hypotheses that the combination will increase the PFS rate to 23% under identical conditions, recruiting a total of 30 patients with NSCLC in a single arm design will give 82% power and 10% 1-side significant level.

The survival rate of NSCLC patients will also be analysed at one year. In addition to reporting the proportion of patients alive at 12 months, a Kaplan Meier curve will be plotted with 95% CI together with median survival provided.

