2.2.1.6 Efficacy

Thirteen Phase II studies investigated the efficacy of vandetanib in patients with advanced or metastatic solid tumours or patients who had failed therapy (medullary thyroid cancer [MTC] (2), prostate cancer (1), colorectal cancer (2), breast cancer (3), NSCLC (4), small cell lung cancer (1)).

In Phase II NSCLC studies, there was an increase in progression-free survival (PFS) for patients treated with vandetanib compared to gefitinib (median PFS 11 weeks vs. 8.1) [6474IL/0003] (Natale *et al* 2009), patients treated with vandetanib plus docetaxel compared to docetaxel alone (approx 18 weeks vs 12) [6474IL/0006] (Heymach *et al* 2007). However, in a study comparing patients treated with vandetanib in addition to paclitaxel plus carboplatin with paclitaxel plus carboplatin alone, the median PFS was similar in both groups (24.0 weeks vs. 23.1) [6474IL/0007]. In a randomized double-blind dose-finding study, the objective response rate was 17.6% in the 100-mg group, 5.6% in the 200-mg group and 16.7% in the 300-mg group [D4200C00039].

In Phase III NSCLC studies (see current version of the vandetanib IB), there was a statistically significant advantage in PFS and time to deterioration of disease-related symptoms (TDS) for the addition of vandetanib to docetaxel compared with docetaxel alone (D4200C00032) (Herbst *et al* 2009). There was a trend for PFS in favour of vandetanib in combination with pemetrexed compared with pemetrexed alone, although this did not reach statistical significance (D4200C00036) (De Boer *et al* 2009), but the combination showed a statistically significant advantage in the disease control rate (DCR). Neither study showed a significant advantage in overall survival (OS) as a consequence of adding vandetanib to

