standard chemotherapy. In a comparison with erlotinib, PFS and OS were similar for vandetanib (D4200C00057). There was a statistically significant improvement for vandetanib over placebo (both in combination with best supportive care [BSC]) for PFS and DCR; however, OS was similar for vandetanib and placebo (D4200C00044). In a Phase III study in patients with unresectable locally advanced or metastatic MTC for whom no standard therapeutic option was available. (D4200C00058), there was a statistically significant improvement in PFS for vandetanib compared with placebo. The AVAiL study which combined bevacizumab with carboplatin/paclitaxel also did not show an increase in overall survival but did show an increase in PFS (Reck *et al* 2009).

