2.3 Rationale for the proposed trial

2.3.1 Proposed Combination Hypothesis for Vandetanib and Selumetinib

The proposed combination hypothesis is that combined inhibition of VEGF, EGF and MEK signalling in an unselected NSCLC patient population (refractory to first-line therapy) may deliver greater benefit than inhibition of any of these targets alone.

The primary aim of the expansion cohort is to demonstrate the effective targeting of EGFR, VEGF and MEK signal transduction through pharmacodynamic end points. The study is not powered sufficiently to deliver definitive clinical efficacy data and thus it is not essential to enrol a homogenous patient population. However, it would be important to have imaging and biomarker evidence to test the rationale of multiple pathway inhibition. Inclusion of patients, for example, who have had previous EGFR targeted therapy (and would normally be resistant to EGFR Tyrosine Kinase Inhibitors (TKIs)) and those who are EGFR TKI naïve and properly informed would be helpful. Having a less restrictive inclusion criteria would also significantly enhance the recruitment rate.

Inhibition of EGFR signalling has been shown to benefit NSCLC patients with activating mutations in the EGFR tyrosine kinase domain or those with high EGFR gene copy number (Mok *et al.*; 2009). There is mounting evidence that NSCLC patients with mutant *KRAS* are less likely to respond to EGFR signalling inhibition (Roberts *et al.*; 2010). The correlation is even more clear-cut in metastatic colorectal cancer where patient tumours containing *KRAS* mutations clearly do not respond to treatment with the anti-EGFR monoclonal antibodies cetuximab or panitumumab. This resistance is presumed to be due to the activation of pathways downstream of RAS such as MEK/ERK being driven by the mutant *KRAS* rather than the EGFR. Conversely, preclinical data indicates that tumour cell lines and human tumour xenografts with *BRAF* or *KRAS* gene mutations tend to be sensitised to MEK inhibition, because of their constitutive activation and dependency on ERK pathway signalling. However, some tumour cell lines have been identified (head and neck squamous cell carcinoma and colorectal carcinoma cells) that lack *BRAF* or *KRAS* gene mutation yet retain sensitivity to MEK inhibition, and these also tend to be sensitive to EGFR tyrosine kinase inhibitors.

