4.1.1 Inclusion criteria

1. **(Dose escalation cohorts)** Histologically or cytologically proven solid tumour for which no conventional therapy exists or is declined by the patient
2. **(Expansion cohort only)** Histologically or cytologically confirmed NSCLC patients only, for which no conventional therapy exists or is declined by the patient.
 - If only cytologically confirmed, baseline biopsy is mandatory for a patient to be eligible.
 - For NSCLC patients to be eligible for the expansion cohort they must have received:
 - One prior line of chemotherapy and/or
 - Previous platinum based chemotherapy and/or
 - At least one previous EGFR inhibitor
3. **(Expansion cohort only)** Measurable disease according to RECIST criteria Version 1.1
4. Life expectancy of at least 12 weeks
5. World Health Organisation (WHO) performance status of 0-1 (Appendix 1)
6. Baseline LVEF $\geq 50\%$
7. Haematological and biochemical indices within the ranges shown below. These measurements must be performed within one week (Day -7 to Day -1) before the patient goes on study.

Laboratory Test	Value required
Haemoglobin (Hb)	≥ 9.0 g/dL
Absolute neutrophil count	$\geq 1.5 \times 10^9$ /L
Platelet count	$\geq 100 \times 10^9$ /L
Normal serum calcium (adjusted)*	2.15-2.55 mmol/L
Normal serum magnesium*	0.60-1.0 mmol/L
Normal serum potassium	≥ 4.0 mmol/L
Either: Serum bilirubin	$\leq 1.5 \times$ upper limit of normal (ULN) This does not apply to patients with Gilbert's disease.
Or: Alanine amino-transferase (ALT) or aspartate amino-transferase (AST) and alkaline phosphatase (ALP)	$\leq 2.5 \times$ ULN unless raised due to liver metastases in which case up to 5 x ULN is permissible
Either: Calculated creatinine clearance (using the Wright or C&G formula)	> 50 mL/min
Or: Isotope clearance measurement**	≥ 50 mL/min (uncorrected)
INR or aPTT***	$< 1.5 \times$ ULN

*or normal range according to the local laboratory

** Isotope clearance result to be used to confirm eligibility if calculated C&G/Wright method results in GFR of $= 50$ mL/min.

*** Therapeutic INR values (2.0-3.0) are acceptable to confirm eligibility for patients who are taking concomitant warfarin.

8. 18 years or over

9. Ability to swallow and retain oral medications.
10. Written (signed and dated) informed consent and be capable of co-operating with treatment, and follow-up

4.1.2 Exclusion criteria:

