7.2.3 Evaluations for Cycle 3 onwards

Required for dose escalation and expansion cohorts

- **Cycle 3 Day 1:** Ophthalmological exam (as per 7.1.2) (within 7 days prior to Cycle 3 Day 1 is acceptable).

On the first day of each cycle (-3 days allowable), prior to dosing

- Physical examination: symptom-directed physical examination.
- WHO performance status, temperature, pulse rate and BP (sitting) and weight.
- Haematology tests: detailed in Section 7.1.4;
- Biochemistry tests: detailed in Section 7.1.4;
- Ophthalmological exam (as per 7.1.2) (for patients experiencing visual disturbances), as clinically indicated. ECG

7.2.4 Evaluations (radiological) at Week 10

- The first radiological assessment of disease (to include thoracic CT in expansion cohort) should be performed following completion of Cycle 2 of combination treatment i.e. Week 10. Radiological assessment to be performed every two cycles thereafter.

Expansion cohort (Cycle 1) ONLY

- [REDACTED]

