10.2 Timing and type of tumour assessments

A thorough clinical and radiological evaluation of malignancy, as judged appropriate by the Investigator, and in line with the protocol, must be performed before starting the investigational medicinal product (IMP). The same methods that detect evaluable lesions at baseline must be used to follow these lesions throughout the trial. To ensure compatibility, the radiological assessments used to assess response must be performed using identical techniques. Imaging based evaluation is preferred to evaluation by clinical examination when both methods have been used to assess the anti-tumour effect of a treatment.

All radiological assessments must be performed within four weeks before starting treatment. The interval between the last anti-cancer therapy and these measurements must be at least four weeks (28 days). All clinical measurements to assess response must be done within **one** week before the patient starting treatment.

All complete (CR) and partial responses (PR) must be confirmed by two consecutive observations not less than four weeks apart. All stable disease (SD) must be confirmed by two consecutive observations not less than six weeks apart.

Copies of the scans must be available for external independent review if requested by the Centre for Drug Development (CDD).

Baseline evaluations

These must include radiological measurements as indicated (chest computerised tomography (CT) scan, abdominal CT scan, magnetic resonance imaging (MRI), bone scan) and/or clinical measurements as appropriate. All areas of disease present must be documented (even if specific lesions are not going to be followed for response) and the measurements of all measurable lesions must be recorded clearly on the scan reports. Any non-measurable lesions must be stated as being present. For clinical measurements, documentation by colour photography including a ruler to estimate the size of the lesion is strongly recommended, as this aids external independent review of responses. (See Section 1.2.1 of RECIST (version 1.1) criteria)

Evaluations during and at 'off-study'

Tumour assessments must be repeated every six weeks or more frequently, when clinically indicated. All lesions measured at baseline must be measured at every subsequent disease assessment, and recorded clearly on the scan reports. All non-measurable lesions noted at baseline must be noted on the scan report as present or absent.

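### The 12-week PFS test rests on an unsourced 9% vandetanib-alone rate that is hard to reconcile with the protocol's own 11-week median, so a positive result could not be credited to selumetinib

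*Protocol*

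**What the plan says.** Protocol Section 13 fixes the null, the alternative and the sample size for 12-week PFS in the NSCLC expansion cohort: "Assuming that the PFS rate in vandetanib alone is 9%, to test the hypotheses that the combination will increase the PFS rate to 23" per cent. It pairs these with 30 patients in a single arm, 82% power and a one-sided 10% level. It cites nothing for the 9% and states no cut-off.

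Section 2.2.1.6 reports a Phase II NSCLC comparison with longer PFS for "patients treated with vandetanib compared to gefitinib (median PFS 11 weeks vs. 8.1" weeks. This is the only median PFS printed there for vandetanib given alone in NSCLC. The other PFS medians in that section are for vandetanib added to chemotherapy. Two Phase III monotherapy comparisons are described without PFS values; one reads "In a comparison with erlotinib, PFS and OS were similar for vandetanib (D4200C00057", and the other is against placebo.

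Section 2.3.1 wants a mixed cohort, including patients "who have had previous EGFR targeted therapy (and would normally be resistant to EGFR Tyrosine Kinase Inhibitors (TKIs)) and those who are EGFR TKI" naive. Section 4.1.1 lists "At least one previous EGFR inhibitor" as one of several and/or routes to entry. Section 2.3.1 also says: "The study is not powered sufficiently to deliver definitive clinical efficacy data".

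**The concern.** In a single-arm test the null rate carries the whole comparison. If 9% is well below what vandetanib alone would achieve in these patients, rejecting it shows only that they did better than 9%. It does not show that selumetinib added anything, which is the hypothesis Section 13 sets out to test.

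The background section suggests that 9% is low. In the cited trial about half of the vandetanib patients were still progression-free at 11 weeks, one week before this trial's time point. Even the 23% target lies below what that median suggests for vandetanib alone. The protocol does not discuss the gap.

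This is the only hypothesis test and power statement visible in the protocol (parts are redacted), and the only visible power-based reason for 30 patients.

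**Working it through.** **Step 1. Reproduce the stated power.** Inputs from Section 13: p0 = 0.09, p1 = 0.23, n = 30, one-sided alpha 0.10 (z = 1.2816).

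Power = Φ{[√n(p1 − p0) − z√(p0(1 − p0))] / √(p1(1 − p1))} = Φ{(0.7668 − 0.3668) / 0.4208} = Φ(0.951) = 82.9%.

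This agrees with the stated 82%.

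**Step 2. Derive the cut-off, since none is stated.** The normal approximation places it at 30 × 0.09 + 1.2816 × √(30 × 0.09 × 0.91) = 2.70 + 2.01 = 4.71 patients, so at least 5 of 30. Exact binomial results:

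| Rule | Alpha at 9% | Power at 23% |
|---|---|---|
| at least 5/30 | 12.8% | 85.2% |
| at least 6/30 | 4.8% | 71.9% |

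At least 6 of 30 is the smallest cut-off that respects the 10% level exactly, so it is the main rule below.

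**Step 3. What an 11-week median implies at week 12.** Assume a Weibull curve through the median, S(t) = 0.5^((t/11)^k).

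| Shape k | S(12) |
|---|---|
| 1 (constant hazard) | 46.9% |
| 2 | 43.8% |
| 3 | 40.7% |
| 5 | 34.3% |

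To reach 9% at week 12 the shape would have to be ln[ln(1/0.09)/ln 2] / ln(12/11) = 14.3. Without a model: going from 50% at week 11 to 9% at week 12 means that 1 − 0.09/0.50 = 82% of those still progression-free fail within one week. Observed PFS curves step down at scans, so these figures are indicative only.

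**Step 4. Does this trial's scan timing explain 9%?** Section 7.2.4 says the first scan "should be performed following completion of Cycle 2 of combination treatment i.e. Week 10". If that scan decides week-12 status, the relevant value is S(10), which is 53% at k = 1 and 65% at k = 5. Section 10.2 instead says "Tumour assessments must be repeated every six weeks or more frequently, when clinically indicated"; a scan then falls at week 12 and Step 3 applies. Neither schedule brings the rate near 9%.

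**Step 5. How often a combination that adds nothing would pass.** Exact binomial, n = 30, with the true rate equal to the vandetanib-alone rate:

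| True rate | at least 6/30 | at least 5/30 |
|---|---|---|
| 9% | 4.8% | 12.8% |
| 15% | 29% | 48% |
| 20% | 57% | 74% |
| 30% | 92% | 97% |

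The pass probability reaches 50% at a true rate of 18.7% (at least 6) or 15.4% (at least 5). Part of the second column's excess comes from that rule already breaking the 10% level at the stated null.

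**The case against.** The strongest reply is that no contradiction has been shown. The 11-week median comes from another trial, and the protocol prints neither its population nor its dose and scan schedule. Section 13 speaks of identical conditions, and this cohort could well do worse. Section 4.1.1 restricts it to patients with no conventional option left or who decline one, EGFR-pretreated patients are admitted, and Section 5.1.1 warns that progression in NSCLC patients may be fast. All of this stands. It supports a rate below 34% to 47%, but the protocol neither uses it to derive 9% nor states an expected case mix.

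A reader might go further and infer that the true vandetanib-alone rate is about 47%, that 9% is therefore false, and that the test is almost certain to pass. The documents do not support that. It would carry a smooth curve from a different trial into a cohort that may be sicker.

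It can also be said that the consequence is small. PFS at 12 weeks is secondary, no dose, stopping or go/no-go rule visibly uses the test, and Section 2.3.1 disclaims definitive efficacy. This lowers the importance. It does not justify the null: limited precision and a benchmark set too low are different faults, and Section 13 still states a formal test with power.

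Finally, the cut-off may be set in the statistical analysis plan. Its absence is not the complaint, which is why both rules are shown and the exact one within 10% is preferred.

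**Conclusion.** The point holds as one about an unjustified benchmark. The 9% null has no source and is hard to reconcile with the only vandetanib-monotherapy NSCLC median that the protocol prints. Unless it is justified, a positive test could not be read as benefit from adding selumetinib.

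The conclusion does not need 34% to 47% to be right for this cohort. A true vandetanib-alone rate of 18.7% is enough for a useless combination to pass half the time under the exact rule, and 15.4% under the normal-approximation cut-off; the intended rate is at most 10%. It rests on two assumptions: independent binary outcomes in 30 analysed patients, and one of the two derived cut-offs. Whether the true rate is that high is not established by the documents.

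The power arithmetic is correct. Importance is moderate: this should be fixed, but no visible trial decision depends on it.

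**What to change.** **Preferred.** Replace the test sentence in Section 13 with a descriptive statement: the 12-week PFS rate will be reported with its exact 95% confidence interval and will not be interpreted as superiority over vandetanib alone. As a guide to precision, 7 of 30 (23%) gives a Clopper-Pearson interval of 10% to 42%. This agrees with Section 2.3.1 and with the descriptive presentation in Section 13.1.

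**If the test is kept.** Give a source for the vandetanib-alone rate, reconcile it with Section 2.2.1.6 and the expected case mix, and restate what 30 patients can show. Illustration only, exact binomial:

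| Null | Rule | Alpha | True rate for 80% power |
|---|---|---|---|
| 20% | at least 10/30 | 6.1% | 39% |
| 30% | at least 13/30 | 8.4% | 49% |

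Neither null is proposed as correct; the sponsor must source it. On the same exact basis, at least 6/30 against 9% has 80% power at 25%. The detectable gain is thus 16 points now (25 − 9) and 19 points against either illustrative null (39 − 20, 49 − 30).

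**Cost.** The preferred change is wording only and adds no patients. The price is a weaker efficacy claim and the loss of the power statement as a reason for 30 patients. The targets in Section 3.2.2, at least 20 patients with full imaging and at least 10 biopsied, remain as a rationale.

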1.2 Clinical trial objectives and endpoints**Primary objectives and endpoints**

Primary objectives	Endpoints
Assessing the safety and toxicity profile of the combination of vandetanib and selumetinib.	Determining causality of each adverse event to vandetanib or selumetinib and grading severity according to NCI CTCAE Version 4.02
To propose a recommended dose and schedule for Phase II evaluation of the combination of vandetanib and selumetinib.	Determining the MTD of the combination of vandetanib and selumetinib as proposed by the protocol. OR the single agent recommended Phase II dose (RP2D) of vandetanib in combination with the single agent RP2D of selumetinib.

Secondary objectives and endpoints

Secondary objectives	Endpoint
Determine the plasma pharmacokinetic (PK) profiles of vandetanib and selumetinib and their metabolites	PK parameters during Cycle 1 including Cmax and AUC pre and post treatment with vandetanib alone and following the combination of vandetanib and selumetinib. Parameters to be measured include: 
• vandetanib• selumetinib and N-desmethyl metabolite. (other metabolites may be measured as determined during the study).
Expansion cohort To evaluate progression free survival (PFS) of patients with NSCLC after treatment with the combination of vandetanib and selumetinib.	Determine PFS at 12 weeks (measured from date of first dose of vandetanib) by RECIST (Response Evaluation Criteria In Solid Tumors) criteria.
Expansion cohort To evaluate the survival rate of patients with NSCLC after treatment with the combination of vandetanib and selumetinib.	Determine the one year survival rate.
Expansion cohort To assess the tumour metabolism in patients with NSCLC.	Measurement of tumour metabolism using CT FDG-PET imaging during Cycle 1 pre and post treatment with vandetanib alone and following the combination of vandetanib and selumetinib.

Tertiary objectives and endpoints

Tertiary objectives	Endpoint
[REDACTED]	[REDACTED]

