If not all data are available from at least three patients in order to take a decision on dose escalation but an eligible patient is ready to begin treatment, the dose level will remain the same. Up to 6 patients may be enrolled at that dose level.

In the event of two patients experiencing a DLT at the first dose level, the dose level may be de-escalated following discussion of all the relevant toxicity data between the Sponsor and the Study Team, including the Chief Investigator.

Dose escalation meetings will be held to determine if it is safe to escalate the dose to the next level. These reviews will be triggered when sufficient patients have had the opportunity to complete the first cycle of combination treatment.

The safety data including a list of DLTs and all AEs will be reviewed along with all other available data by the Sponsor, CI and PI(s). The decision to dose escalate or expand a cohort will be communicated to all investigator sites by the Sponsor.

It is not anticipated that smaller dose escalations or de-escalations will be employed but would need to be considered if there is a large difference in the number of DLTs in two adjacent dose levels.

Following completion of the dose escalation phase, a review of the data will be performed by the Sponsor (to include review by the Protocol, Safety and Review Board (PSRB) before approval is granted by the Sponsor that the expansion cohort can be opened.

Once the MTD of the combination has been determined the expansion cohort will commence. The MTD determined in this cohort will be the dose level of the combination recommended for Phase II trials.

Expansion cohort.

Up to 30 patients with NSCLC will be enrolled to the expansion cohort. All patients will be treated with the combination of vandetanib and selumetinib. The dose of vandetanib and selumetinib will be the RP2D which will be determined in the dose escalation stage of the study.

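### With 30 patients, no exact cut-off gives the stated 82% power at 10% one-sided alpha: the choices are 72% power at 4.8% or 85% at 12.8%

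*Protocol*

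**What the plan says.** Section 13 of the Protocol (Data analysis and statistical considerations) takes the 12-week PFS rate on vandetanib alone to be 9% and sets out to test whether "the combination will increase the PFS rate to 23% under identical conditions". It then states that "recruiting a total of 30 patients with NSCLC in a single arm design will give 82% power and 10% 1-side significant level".

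The endpoint is defined in Section 1.2, and again in Section 3.1, as a status at a fixed time: "Determine PFS at 12 weeks (measured from date of first dose of vandetanib) by RECIST". Section 5.3 gives the cohort size as a ceiling: "Up to 30 patients with NSCLC will be enrolled to the expansion cohort". Sections 1.3 and 1.4.4 say approximately 30.

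Section 13 gives no formula, test or cut-off for this comparison. The Kaplan-Meier curve it mentions is for survival, not for 12-week PFS.

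**The concern.** The sentence states two operating characteristics as facts about the design. With a null rate of 9% and 30 patients, the expected number of successes under the null is 30 × 0.09 = 2.7. At so small a count a normal approximation is unreliable, and moving the cut-off by one patient changes the error rates by several points. An exact calculation should then show whether any whole-number rule reaches the stated pair.

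Two things are at stake. First, a reader would credit the cohort either with a lower false-positive risk or with more power than it has. Second, the result 5 of 30 is left open: one common reading of a 10% one-sided test calls it a success and an exact test does not.

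**Working it through.** **Inputs, all from Section 13:** null rate p0 = 0.09; alternative rate p1 = 0.23; n = 30, single arm; one-sided alpha 0.10; stated power 82%.

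**1. Reproducing the stated figure.** The one-sample normal approximation, with the null variance for the critical value and the alternative variance for power, is

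power = Φ{[√n·(p1 − p0) − z₀.₉₀·√(p0(1 − p0))] / √(p1(1 − p1))}

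= Φ{[√30 × 0.14 − 1.2816 × √(0.09 × 0.91)] / √(0.23 × 0.77)}

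= Φ{(0.7668 − 0.3668) / 0.4208} = Φ(0.951) = 82.9%.

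The arcsine version gives 80.5%, and a continuity correction gives 76.8%. So 82% lies within two points of two standard large-sample formulas. It is not a slip in applying them.

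**2. Exact binomial.** Let X be the number progression-free at 12 weeks, X ~ Bin(30, p), with success if X ≥ r. Alpha is P(X ≥ r | 0.09) and power is P(X ≥ r | 0.23).

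| Success if X ≥ | Exact alpha | Exact power |
|---|---|---|
| 4 | 28.3% | 93.8% |
| 5 | 12.8% | 85.2% |
| 6 | 4.8% | 71.9% |
| 7 | 1.5% | 55.3% |

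The smallest cut-off with alpha at or below 10% is 6, and its power is 71.9%. The largest cut-off with power of at least 82% is 5, and its alpha is 12.8%. No row meets both conditions.

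**3. What a nominal z-test would do.** With the null variance, as in the formula of step 1, z = (x/30 − 0.09)/√(0.09 × 0.91/30).

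- At x = 4, z = 0.83, below 1.28.
- At x = 5, z = 1.47, above 1.28.

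This test rejects at 5 of 30, so its true type I error is 12.8%. If the variance is estimated from the data instead, z = 1.13 at 5 of 30 and 1.51 at 6 of 30, and the test rejects only from 6. The exact test at 10% also needs 6. The sentence in Section 13 therefore does not settle what 5 of 30 means.

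**4. How much is discreteness.** A randomised test attains exactly 10% by rejecting at X = 5 with probability (0.1000 − 0.0481)/(0.1277 − 0.0481) = 0.652. Its power is 0.7192 + 0.652 × (0.8525 − 0.7192) = 80.6%. Most of the shortfall thus comes from the gap between attainable alphas and only a little from the approximation itself, but a trial would not normally be read with a randomised rule.

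**5. Sensitivity to the cohort size.** The best exact power with alpha at or below 10% is:

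| n | Cut-off | Alpha | Power |
|---|---|---|---|
| 27 | 5 | 9.0% | 77.8% |
| 28 | 6 | 3.6% | 65.0% |
| 29 | 6 | 4.2% | 68.6% |
| 30 | 6 | 4.8% | 71.9% |
| 31 | 6 | 5.5% | 75.0% |
| 32 | 6 | 6.3% | 77.8% |
| 33 | 6 | 7.1% | 80.4% |
| 34 | 6 | 8.0% | 82.7% |

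The first sample size that meets both stated figures is 34.

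**The case against.** The strongest reply has four parts.

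- **It is a planning approximation, not an arithmetic error.** This is fair as to origin: standard formulas give 80.5% to 82.9%. Which one was used is not stated, so tracing the 82% to the normal approximation is a likely inference and no more. It does not make the stated pair attainable.
- **The 10-point gap compares tests of different stringency.** This is also fair. The 71.9% belongs to a test at 4.8%, and at exactly 10% the power would be 80.6%. But that operating point needs a randomised decision at 5 of 30. Among usable rules the choice is between 72% power and a 12.8% alpha.
- **The test and cut-off may sit in a statistical analysis plan, and a Kaplan-Meier estimate would not be tied to whole numbers.** The absence of a cut-off is not in itself the complaint. A plan can choose a rule, but no count rule on 30 patients makes both stated figures true. Section 13 frames the endpoint as a rate at 12 weeks and describes no Kaplan-Meier test for it.
- **The consequence is modest.** PFS is a secondary endpoint. Section 2.3.1 says that the trial lacks the power for definitive efficacy conclusions and gives the expansion cohort a pharmacodynamic aim. Sections 13.1 and 13.5 describe descriptive presentation and listings. No decision rule in the Protocol depends on this test. All of this stands and limits the weight of the point. It does not correct figures that the Protocol chose to state as the statistical basis for 30 patients.

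**Conclusion.** The point holds. On the Protocol's own inputs, 30 patients cannot give 82% power at a 10% one-sided level with any whole-number cut-off. If alpha is kept within 10%, power is 71.9%, about 10 points lower, and the risk of missing a true 23% rate is 28.1% instead of 18%. If 5 of 30 counts as success, power is 85.2% but the type I error is 12.8%, about 28% higher in relative terms than stated.

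This rests on treating 12-week PFS as a yes/no outcome known for all 30 patients, which is the natural reading of Section 13. It is not sensitive to small changes in size: for 27 to 33 patients, exact power at alpha within 10% runs from 65% to 80%. Because the endpoint is secondary, this should be corrected but does not threaten the trial's main objectives.

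**What to change.** In Section 13, name a one-sided exact binomial test and replace the power statement with one of these:

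- success if at least 6 of 30 patients are progression-free at 12 weeks: exact type I error 4.8%, power 72% at a true rate of 23%; or
- success if at least 5 of 30 are progression-free at 12 weeks: exact type I error 12.8%, power 85%.

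The first keeps the 10% limit. The second keeps the power and openly gives up that limit. Either one settles the reading of 5 of 30 before the data are seen. If the 9% null is revised, the exact figures should be given for the new value.

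The cost is one sentence and a less favourable stated power or alpha. No extra patients are needed and trial conduct does not change.
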